12 OCT 2020

dose related, not idiosyncratic, suggesting that a much lower systemic dose achieved with the 100 mg AP01 nebulized dose may have a superior safety profile. The dose response seen in the CAPACITY 004 study suggests that higher local concentrations after aerosol administration may also result in improved efficacy.

### 1.2.3 Known and Potential Risks and Benefits

Pirfenidone has well established animal and human toxicity profiles after oral administration which are dose dependent, including gastrointestinal side effects, photosensitivity, and hepatic dysfunction.

Total systemic absorption anticipated after inhaled administration will be on average 15-fold less than standard 801 mg oral dose, therefore, the known systemic side effects are not expected to present in this study. Liver function tests (AST/ALT) will be monitored throughout the study as an extra precaution, however liver toxicity is not expected due to the low systemic exposure. In the case of an AST or ALT value greater than 5 times the upper limit of normal, an alert will be sent to the site and to the medical monitor informing them of the value and providing further instructions regarding eligibility and assessment for potential adverse events. An AST or ALT value of greater than 5 times the upper limit of normal is exclusionary for enrollment.

In the AP01-001 single ascending dose study, the drug was well tolerated in both normal volunteers and IPF patients. The most commonly reported event was cough, which was noted in 7/38 volunteers and 1/6 IPF patients in the Phase 1 study. Cough was mild, self-limited, and did not prevent the full administration of aerosol dose in any subject. Refer to Table 3 for the full summary of AEs observed in the single aerosol dose AP01-001 Phase 1 study.

Forced expiratory volume in one second (FEV1) values were obtained 10 minutes post-dosing to detect whether the inhaled dose would lead to bronchospasm. One volunteer had a 17% asymptomatic reduction of FEV1 after a 100 mg nebulizer dose, with a post dose FEV1 of 3.9 liters (L). No other subject had a decline greater than 15%.

### 1.2.4 Rationale for Study Design

Oral pirfenidone has been shown to provide improvements in FVC as well as a positive impact on mortality in IPF patients. However, systemic side effects and likely under-treatment of the airways indicate an inhaled formulation has the potential to provide improved tolerability and efficacy profiles. AP01-001, demonstrated that a single dose up to 100 mg/mL was safe and well-tolerated while achieving greatly improved pirfenidone ELF concentrations and reduced systemic levels. AP01-002 is designed to demonstrate AP01 multiple dose safety and tolerability in IPF patients, as well as provide estimates of the variability and effect of AP01 on important efficacy outcomes. The results of AP01-002 will assist in the design of future studies. The preliminary 6 month results from AP01-002 allowed the DSMB to select the optimal dosing regimen of 100 mg twice daily for future AP01 studies.

Avalyn Pharma, Inc.  
AP01-002

Protocol v2.1  
12 OCT 2020

## 2. OBJECTIVES

- To evaluate the safety and tolerability of treatment with AP01 when given either once or twice daily to patients with IPF
- To estimate the treatment effect of AP01 given 50 mg once daily and 100 mg twice daily on absolute change in percent predicted FVC in patients with IPF
- To estimate the treatment effect of AP01 given 50 mg once daily and 100 mg twice daily on absolute change in percent predicted Diffusion Capacity for Carbon Monoxide ( $D_{LCO}$ ) in patients with IPF
- To compare the safety and efficacy of 50 mg once daily vs 100 mg twice daily dosing to provide guidance on dosing regimens for future studies
- To estimate the treatment effect of AP01 given 50 mg once daily and 100 mg twice daily on change in Patient Reported Outcomes (PROs) and cough in patients with IPF
- To estimate the treatment effect of AP01 given 50 mg once daily and 100 mg twice daily on change in the extent of fibrosis and lung volumes as measured by High Resolution Computed Tomography (HRCT) scans in patients with IPF
- To evaluate the following exploratory measurements:
  - Correlation between weekly home spirometry measurements and in-clinic spirometry values
  - Correlation of extent of fibrosis and lung volumes as measured by HRCT at Baseline and Week 24 to other measures of clinical status, e.g. spirometry
  - Change from Baseline in serum biomarkers of alveolar epithelial injury (CA19-9 and CA-125)

Avalyn Pharma, Inc.  
AP01-002

Protocol v2.1  
12 OCT 2020

### **3. STUDY ENDPOINTS**

#### **3.1. Safety Outcome Measures**

- Treatment-emergent AEs
- Change from pre-dose to post-dose FEV1 after initial dose
- Treatment-emergent deaths
- Treatment-emergent changes in clinical laboratory findings
- Changes in vital signs

#### **3.2. Efficacy Outcome Measures**

- Change from Baseline in FVC % predicted
- Change from Baseline in DLCO
- Change from Baseline in Patient Reported Outcomes (PRO)
- Change from Baseline in cough frequency and intensity
- Change from Baseline in extent of fibrosis and lung volumes

#### **3.3. Exploratory Outcome Measures**

- Correlation between weekly home spirometry measurements and in-clinic spirometry values
- Correlation of extent of fibrosis and lung volumes as measured by HRCT at Baseline and Week 24 to other measures of clinical status, e.g. spirometry
- Change from Baseline in serum biomarkers of alveolar epithelial injury (CA19-9 and CA-125)

Avalyn Pharma, Inc.  
AP01-002

Protocol v2.1  
12 OCT 2020

[figure not shown]
## 4. INVESTIGATIONAL PLAN

### 4.1. Study Design

This Phase 1b, 2-part, open-label study of AP01 will randomize approximately 100 patients with IPF. Patients will be randomized in a 1:1 ratio to one of two treatment arms: 50 mg day once daily or 100 mg twice daily. The primary objective is to evaluate safety and tolerability of treatment with AP01 by monitoring AEs and post-dose spirometry. This study will also evaluate the effect of AP01 on various efficacy measures as detailed in Section 2.

[figure not shown]
#### **Figure 1: Part A Study Schema**

**PART A – Patients are randomized at Visit 2 to either 50 mg given once daily or 100 mg AP01 given twice daily**

#### **Figure 2: Part B Study Schema**

**PART B – Patients continue randomized treatment regimen of either 50 mg once daily or 100 mg AP01 twice daily**

In Part A, eligible patients at least 40 years of age with a confident clinical and radiographic diagnosis of IPF according to pre-specified criteria,  $40 \leq \%FVC \leq 90$ ,  $FEV_1/FVC$  ratio  $\geq 70\%$  and  $30 \leq \%DL_{CO} \leq 90$  will be randomized with equal probability to receive AP01 50 mg once daily or 100 mg twice daily for 24 weeks. Other than brief periods of medically appropriate treatment for acute IPF exacerbation, patients will not receive any other therapy for the treatment of IPF during Part A. If in the opinion of the investigator, a patient is in need of treatment with oral pirfenidone or nintedanib during Part A, the patient should be discontinued from the study and return to the clinic for their Early Termination visit. Supplemental oxygen will be allowed during the entire study.

Avalyn Pharma, Inc.  
AP01-002

Protocol v2.1  
12 OCT 2020

The initial dose of drug will be administered in the clinic to confirm airway tolerance. If based on the investigator's opinion, the patient had tolerability issues during the first dose administration, a second dose, at least 4 hours later, will also be observed. Patients who experience cough that limits their ability to complete dosing will be given 1 - 2 puffs (90 - 100 micrograms ( $\mu\text{g}$ )) of salbutamol in order to complete the in-clinic dose. These patients, as well as patients with a history of asthma or smoking history of 20 pack years or greater, or patients that have a  $\geq 15\%$  drop in FEV1 percent predicted in their pre-dose and post-dose readings will be required to use 1 - 2 puffs (90 - 100  $\mu\text{g}$ ) of salbutamol prior to dosing throughout the study unless these patients are currently taking a long-acting beta-2-agonist therapy.

Patients will have a telephone assessment at Week 1 and in-clinic assessments at Weeks 4, 8, 12, 16, 20, and 24. The Data and Safety Monitoring Board (DSMB) will perform a review of safety data from the first 20 patients after Week 4 to confirm the safety and airway tolerability of multiple dose administration. A decision to stop, continue or modify the study will be made based on this review.

Part B will collect long term safety and efficacy data for an additional 48 weeks. Patients who complete Part A through Week 24 and, in the opinion of the investigator are compliant with treatment, may select to continue the treatment to which they were randomized. The DSMB for this study met on 12 OCT 2020 to review preliminary dose comparison data. It was determined that the 100 mg twice daily dose showed a trend for amelioration of FVC loss and recommended all patients in Part B be treated with the 100 mg twice daily dose. Therefore, all patients who participate in Part B after the implementation of this amendment will be treated with the 100 mg twice daily dose. Patients participating in the AP01-005 study will continue treatment that they are receiving at Visit 12 on this study and then transition to the Rollover study upon approval of AP01-005 at their site.

Study duration is up to 80 weeks for patients that complete both Part A and Part B of the study and up to 92 weeks for patients that plan to continue AP01 on the AP01-005 Rollover study. If patients discontinue study treatment prior to Week 72 for any reason, they should return to the site for an Early Termination visit. All patients who complete the regular study visits through Week 72 in Part B will return for a Follow-up visit 28 days after their End of Study visit unless the patient plans to participate in AP01-005. Patients planning to enroll in AP01-005 will continue administering AP01 using EOS/Visit 12 as their Baseline visit for AP01-005. If Regulatory approval for AP01-005 has not been achieved by the time a patient is ready to enroll in AP01-005, the patient will continue treatment that they are receiving at Visit 12 on this study and then transition to the Rollover study upon approval of AP01-005 at their site. Patients will have a visit to assess safety and compliance at least every 3 months while awaiting approval of AP01-005 at their site. The end of the study for all patients will be the day of their last Follow-up or Early Termination visit or their last treatment visit for those enrolling in AP01-005.

Avalyn Pharma, Inc.  
AP01-002

Protocol v2.1  

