12 OCT 2020

- HRCT (If not performed at Screening or Screening HRCT was performed more than 1 month prior to Baseline. For scheduling purposes, the Baseline HRCT may be performed up to 1 month prior to or 1 week after the Baseline visit.)
- Pre-dose Spirometry and  $D_{LCO}$
- Pre-dose  $SaO_2$ ; Patients with  $SaO_2 < 90\%$  will be administered supplemental oxygen until the  $SaO_2$  reaches 93% prior to dosing
- Blood samples for laboratory tests (Chemistry including AST and ALT, Hematology, Biomarkers (CXCL13, CCL18, MMP3, CA19-9 and CA-125)
- Urinalysis
- Urinary pregnancy test (FOCBP only)
- Confirm Inclusion/Exclusion criteria
- Randomization
- Study material training and first study drug administration; patients experiencing excessive cough or bronchospasm will be administered 1 – 2 puffs (90 - 100  $\mu$ g) of salbutamol prior to subsequent doses or during initial dosing
- Post-dose Spirometry to be performed  $\leq 10$  minutes after completion of AP01 dose (Patients with a  $\geq 15\%$  drop from pre-dose spirometry who are symptomatic will be treated as described in section 8.6.)
- Post-dose  $SaO_2$
- Study material dispensation, including salbutamol and instructions for use of salbutamol (if needed as described in Sections 8.6 and 8.7.)
- Home spirometry training and dispensation

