### **8.6. Investigational Drug Administration**

Patients will be trained on use of the eFlow and administration of the study drug at the Baseline visit. The first dose of study drug for each patient will be administered and observed at the clinical study site at the Baseline visit to confirm tolerability. All subsequent doses will be administered by the patient at home. All doses must be taken at least 4 hours apart.

Patients who experience cough that limits their ability to complete dosing will be given 1 – 2 puffs (90 - 100 µg) of an inhaled beta 2 agonist, such as salbutamol, in order to complete the in-clinic dose. These patients, as well as patients with a history of asthma or smoking history of 20 pack years or greater, or patients that have a  $\geq 15\%$  drop in FEV1 percent predicted in their pre-dose and post-dose readings and are symptomatic will be provided with and required to use 1 - 2 puffs (90 - 100 µg) of salbutamol prior to their second dose and for dosing throughout the study, unless these patients are currently taking a long-

Avalyn Pharma, Inc.  
AP01-002

Protocol V2.1  

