**Figure 2: Part B Study Schema**

PART B – Patients continue randomized treatment regimen of either 50 mg once daily or 100 mg AP01 twice daily

In Part A, eligible patients at least 40 years of age with a confident clinical and radiographic diagnosis of IPF according to pre-specified criteria, $40 \leq \%FVC \leq 90$, forced expiratory volume in 1 second (FEV_1)/FVC ratio $\geq 70\%$ and $30 \leq \%DL_{CO} \leq 90$ will be randomized with equal probability to receive AP01 50 mg once daily or 100 mg twice daily for 24 weeks. Other than brief periods of medically appropriate treatment for acute IPF exacerbation, patients will not receive any other therapy for the treatment of IPF during Part A. If in the opinion of the investigator, a patient is in need of treatment with oral pirfenidone or nintedanib during Part A, the patient should be discontinued from the study and return to the clinic for their Early Termination visit. Supplemental oxygen will be allowed during the entire study.

The initial dose of drug will be administered in the clinic to confirm airway tolerance. If based on the investigator's opinion, the patient had tolerability issues during the first dose administration, a second dose, at least 4 hours later, will also be observed. Patients who experience cough that limits their ability to complete dosing will be given 1 - 2 puffs (90 - 100 microgram (μg)) of salbutamol in order to complete the in-clinic dose. These patients, as well as patients with a history of asthma or smoking history of 20 pack years or greater, or patients that have a $\geq 15\%$ drop in FEV_1 % predicted in their pre-dose and post-dose readings will be required to use 1 - 2 puffs (90 - 100 μg) of salbutamol prior to

This document is confidential.

SAP Version: 3.0 (15JUL2021)
Controlled Document ID: **3903A.01**, Effective Date 29-Oct-2018
Filing requirements: TMF

Page 13 of 52

Statistical Analysis Plan

Sponsor: Avalyn Pharma, Inc.; Protocol No.: AP01-002

dosing throughout the study unless these patients are currently taking a long-acting beta-2-agonist therapy.

Patients will have a telephone assessment at Week 1 and in-clinic assessments at Weeks 4, 8, 12, 16, 20, and 24. The DSMB will perform a review of safety data from the first 20 patients after Week 4 to confirm the safety and airway tolerability of multiple dose administration. A decision to stop, continue or modify the study will be made based on this review.

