3.7. Administration of Study Medication

Patients will be trained on use of the eFlow and administration of the study drug at the Baseline visit. The first dose of study drug for each patient will be administered and observed at the clinical study site at the Baseline visit to confirm tolerability. All subsequent doses will be administered by the patient at home. All doses must be taken at least 4 hours apart.

Patients who experience cough that limits their ability to complete dosing will be given 1 – 2 puffs (90 -

This document is confidential.

SAP Version: 3.0 (15JUL2021)
Controlled Document ID: **3903A.01**, Effective Date 29-Oct-2018
Filing requirements: TMF

Page 15 of 52

Statistical Analysis Plan

Sponsor: Avalyn Pharma, Inc.; Protocol No.: AP01-002

100 µg) of an inhaled beta 2 agonist, such as salbutamol, in order to complete the in-clinic dose. These patients, as well as patients with a history of asthma or smoking history of 20 pack years or greater, or patients that have a $\geq 15\%$ drop in FEV₁ % predicted in their pre-dose and post-dose readings and are symptomatic will be provided with and required to use 1 - 2 puffs (90 - 100 µg) of salbutamol prior to their second dose and for dosing throughout the study, unless these patients are currently taking a long-acting beta-2-agonist therapy. If symptoms persist with study treatment despite beta-2-agonist therapy, the Investigator will assess and discontinue the patient due to tolerability issues if he/she deems it necessary.

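### The rule on salbutamol before dosing after a first-dose FEV1 fall of 15% or more is written both with and without a symptom condition, so the documents disagree about asymptomatic patients with no other trigger

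*Protocol*

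**What the plan says.** Protocol 4.1, describing the initial in-clinic dose, lists who must take salbutamol before dosing. The list includes patients with a fall of at least 15% in FEV1 "percent predicted in their pre-dose and post-dose readings will be required to use" it, and the requirement runs "prior to dosing throughout the study unless these patients are currently taking a long-acting beta-2-agonist therapy". Symptoms are not mentioned. SAP 3.3 carries the same text: "predicted in their pre-dose and post-dose readings will be required to use".

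Protocol 8.6, the section on drug administration, has the same list with one added condition: "percent predicted in their pre-dose and post-dose readings and are symptomatic will be provided with and required to use" salbutamol "prior to their second dose and for dosing throughout the study". The Day 1 procedures in Protocol 6.2.2 also limit it to patients with a "drop from pre-dose spirometry who are symptomatic will be treated as described in section 8.6". SAP 3.7 follows 8.6: "predicted in their pre-dose and post-dose readings and are symptomatic will be provided with and required to use". SAP 10.6 also attaches the symptom condition to the FEV1 fall.

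The versions otherwise agree. Both require salbutamol for dose-limiting cough, a history of asthma, or 20 or more pack-years, and both exempt patients already on a long-acting beta-2-agonist.

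**The concern.** The instruction is mandatory, concerns airway safety, and applies for as long as the patient is dosed. Protocol 15.2 allows deviations only in an emergency. A site that leaves an asymptomatic patient with a 16% fall untreated complies with 8.6 but not with 4.1.

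The matter also bears on the primary objective. Safety and tolerability are to be judged by adverse events and post-dose spirometry, and the first-dose FEV1 change is a named safety outcome. Whether patients inhale a bronchodilator before later doses affects how their tolerability is read. The planned first-dose table would not show whether sites had applied different versions to the same kind of patient.

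**Working it through.** No figure in the plan depends on this rule, so the check is a comparison of texts, followed by a rough sense of scale.

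**Step 1: the passages side by side**

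| Section | FEV1 fall of 15% or more | Symptoms also required? | Stated timing |
|---|---|---|---|
| Protocol 4.1 | in % predicted | No | before dosing, whole study |
| SAP 3.3 | in % predicted | No | before dosing, whole study |
| Protocol 6.2.2 | from pre-dose spirometry | Yes | refers to 8.6 |
| Protocol 8.6 | in % predicted | Yes | from the second dose, whole study |
| SAP 3.7 | in % predicted | Yes | from the second dose, whole study |
| SAP 10.6 | in % predicted | Yes | before dosing, whole study |

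In 8.6 taken alone, one could ask whether the symptom condition belongs to the FEV1 item or to the whole list. Protocol 6.2.2 and SAP 10.6 state it for the FEV1 fall by itself, which settles the reading.

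**Step 2: who is affected**

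| Patient with a fall of 15% or more | 4.1 / SAP 3.3 | 6.2.2 / 8.6 / SAP 3.7 / SAP 10.6 |
|---|---|---|
| On a long-acting beta-2-agonist | exempt | exempt |
| Not exempt; symptomatic | required | required |
| Not exempt; asymptomatic; dose-limiting cough, asthma history or 20+ pack-years | required | required by the other trigger (8.6, SAP 3.7) |
| Not exempt; asymptomatic; no other trigger | **required** | **not required** |

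Only the last row conflicts.

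**Step 3: scale, for illustration**

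Protocol 1.2.3 reports: "One volunteer had a 17% asymptomatic reduction of" FEV1 after 100 mg in AP01-001, and no other subject fell by more than 15%. Protocol Table 3 gives 6 active subjects in each of six cohorts, four of them at 100 mg.

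- Among active 100 mg recipients: 1/24 = 4.2% (exact 95% CI 0.1% to 21.1%). In 50 patients: 50 × 1/24 = 2.1 expected, and 1 − (23/24)^50 = 0.88 chance of at least one.
- Among all active recipients: 1/36 = 2.8%. In 50 patients: 50 × 1/36 = 1.4 expected, and 1 − (35/36)^50 = 0.76.

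These count every asymptomatic fall. They do not remove patients with another trigger or on a long-acting beta-2-agonist, for whom the versions agree.

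**Step 4: the unit of the 15%**

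Pre- and post-dose readings are taken on the same day in the same patient, so the predicted value cancels: (pre% − post%)/pre% = (preL − postL)/preL. A relative fall is therefore the same in % predicted and in litres, and 6.2.2 agrees with 8.6 if both are read as relative. They part only if 15% of predicted means percentage points. At an illustrative pre-dose value of 75% predicted, a 15% relative fall is 0.15 × 75 = 11.25 points, whereas 15 points is 15/75 = 20% relative. No section says which is meant.

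**Step 5: what the planned tables show**

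SAP 10.6 counts falls of 15% or more, then those with symptoms, and reports salbutamol only within the symptomatic branch. The number of asymptomatic falls follows by subtraction, but salbutamol use among them does not. SAP 7.5 counts salbutamol before each in-clinic dose. That does not cover salbutamol begun before home doses, which is where a patient with no second observed dose would start it.

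**The case against.** The best reply is that practice probably follows a single version. The Day 1 instructions in Protocol 6.2.2 point to 8.6, and so do the salbutamol references in 8.7 and 8.8.2. None points to 4.1, which is a design overview, and SAP 3.3 is headed as a brief description. This stands as far as it goes: a reader might infer that sites will treat identical patients differently, but the documents support only that they may. It does not remove the contradiction, because no section ranks 4.1 below 8.6 and 4.1 is worded as a requirement.

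A reader might also count three contradictions. The documents support one.

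- **First dose.** For asthma history and 20+ pack-years, 4.1 speaks of dosing throughout the study and 8.6 of the second dose onward. The sentence in 4.1 comes after the account of the initial dose and includes triggers known only once that dose has been given, so it can be read as applying from then on. SAP 7.5 also already tabulates salbutamol taken before the first dose.
- **Unit.** Protocol 6.2.2 defers to 8.6, and a consistent relative reading makes the two agree. The unit is undefined, which is not the same as contradictory.

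The scale is open to the same caution. The single AP01-001 case was a volunteer, and no IPF patient (0 of 6) fell by more than 15%. The volunteer's cohort is not given. One 100 mg cohort consisted of prior or current smokers, so a 20 pack-year trigger cannot be excluded. If the 17% was a relative fall, it reaches 15 points only from a pre-dose value of at least 15/0.17 = 88% predicted. To expect about two affected patients per arm would be to over-read one event.

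Finally, a reader might infer that bronchodilator use distorts the efficacy spirometry. The documents do not fix the timing of salbutamol relative to later clinic spirometry and quantify no effect on FVC, so this is unsupported.

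**Conclusion.** The contradiction on symptoms is real and should be corrected. Two sections require salbutamol after any qualifying FEV1 fall, four require symptoms as well, and nothing decides between them. It concerns a narrow group: asymptomatic, no dose-limiting cough, no asthma history, under 20 pack-years, and not on a long-acting beta-2-agonist. The number is probably small and cannot be estimated reliably from one event in 24 to 36 active subjects; the AP01-001 case shows only that an asymptomatic fall of this size can occur. No sample-size or efficacy figure is affected.

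The first-dose question and the unit of the 15% are ambiguities to clear up in the same edit. The conclusion does not depend on either.

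**What to change.** Reconcile Protocol 4.1, 6.2.2 and 8.6 and SAP 3.3, 3.7 and 10.6 to one identical text that states whether symptoms are required. The choice belongs to the sponsor and its clinical advisers. In the same text, state whether the rule for asthma history and 20+ pack-years covers the first in-clinic dose, and whether the 15% is a relative fall or percentage points.

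In SAP 10.6, name the unit used for the fall. Add, by arm, the number of asymptomatic patients with a fall of 15% or more who were put on salbutamol and the number who were not. For first doses already given, these rows are what would show how the rule was applied.

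The cost is a clarification letter or short wording change, matching SAP text, and two table rows. No new procedure is needed: spirometry and symptom status are already planned for this table, and salbutamol use should be available from the concomitant medication records, where Protocol 8.9.1 has pre-treatment documented.
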